12.5.3 Pharmacokinetics

LNP023 plasma concentration data will be listed by sequence, treatment dose group, subject, and visit/sampling time point.

Commercially Confidential Information

Pharmacokinetic parameters will be calculated from within four weeks of dosing only and will be listed by treatment dose group and subject. Descriptive summary statistics will include mean (arithmetic and geometric), SD, and CV (arithmetic and geometric), median, minimum and maximum. An exception to this is Tmax, where median, minimum and maximum will be presented.

Table 12-1 Non-compartmental pharmacokinetic parameters

| | |
|---------|--|
| AUClast | The AUC from time zero to the last measurable concentration sampling time (tlast) (mass x time x volume-1) |
| AUCtau | The AUC calculated to the end of a dosing interval (tau) at steady-state (amount x time x volume-1) |
| AUCtau | The area under the plasma (or serum or blood) concentration-time curve from time zero to the end of the dosing interval tau at steady state [mass x time / volume] |
| Cmax | The maximum (peak) observed plasma, blood, serum, or other body fluid drug concentration after single dose administration (mass x volume-1) |
| Cmin | The lowest plasma (or serum or blood) concentration observed during a dosing interval at steady state [mass / volume] |
| Tmax | The time to reach maximum (peak) plasma, blood, serum, or other body fluid drug concentration after single dose administration (time) |
| T1/2 | The elimination half-life associated with the terminal slope (l _z) of a semi logarithmic concentration-time curve (time). Use qualifier for other half-lives |

A linear mixed effects model will be fitted to the log-transformed PK parameters (AUC0-24h, AUCinf, and Cmax) as described for dose-response analysis of LDH. For each PK parameter backtransformed estimates and confidence interval will be plotted against dose level.

During modeling of the pharmacokinetics of study treatment, the broad principles outlined in the FDA guidance will be followed (Guidance for Industry: Population Pharmacokinetics; <http://www.fda.gov/cder/guidance/1852fnl.pdf>).

12.6 Analysis of exploratory endpoints

Commercially Confidential Information

12.7 Interim analyses

Commercially Confidential Information

12.8 Sample size calculation

12.8.1 Primary endpoint(s)

With 10 subjects this study has 80% probability to meet the efficacy criteria of 5 or more successful patients out of 10 if the true response rate is 58%.

Commercially Confidential Information

13 Ethical considerations and administrative procedures

13.1 Regulatory and ethical compliance

This clinical study was designed and shall be implemented, executed and reported in accordance with the [ICH Harmonized Tripartite Guidelines](#) for Good Clinical Practice, with applicable local regulations (including European Directive 2001/20/EC, US CFR 21), and with the ethical principles laid down in the Declaration of Helsinki.

13.2 Responsibilities of the investigator and IRB/IEC

Before initiating a trial, the investigator/institution must obtain approval/favorable opinion from the Institutional Review Board/Independent Ethics Committee (IRB/IEC) for the trial protocol, written informed consent form, consent form updates, patient recruitment procedures (e.g., advertisements) and any other written information to be provided to subjects. Prior to study start, the investigator is required to sign a protocol signature page confirming his/her agreement to conduct the study in accordance with these documents and all of the instructions and procedures found in this protocol and to give access to all relevant data and records to Novartis monitors, auditors, Novartis Quality Assurance representatives, designated agents of Novartis, IRBs/IECs, and regulatory authorities as required. If an inspection of the clinical site is requested by a regulatory authority, the investigator must inform Novartis immediately that this request has been made.

13.3 Publication of study protocol and results

The protocol will be registered in a publicly accessible database such as clinicaltrials.gov and as required in EudraCT. In addition, after study completion (*defined as last patient last visit*) and finalization of the study report the results of this trial will be submitted for publication and posted in a publicly accessible database of clinical trial results, such as the Novartis clinical trial results website and all required Health Authority websites (e.g. Clinicaltrials.gov, EudraCT etc.).

For details on the Novartis publication policy including authorship criteria, please refer to the Novartis publication policy training materials that were provided to you at the trial investigator meetings

13.4 Quality Control and Quality Assurance

Novartis maintains a robust Quality Management System (QMS) that includes all activities involved in quality assurance and quality control, to ensure compliance with written Standard Operating Procedures as well as applicable global/local GCP regulations and ICH Guidelines.

Audits of investigator sites, vendors, and Novartis systems are performed by auditors, independent from those involved in conducting, monitoring or performing quality control of the clinical trial. The clinical audit process uses a knowledge/risk based approach.

Audits are conducted to assess GCP compliance with global and local regulatory requirements, protocols and internal SOPs, and are performed according to written Novartis processes

14 Protocol adherence

This protocol defines the study objectives, the study procedures and the data to be collected on study participants. Additional assessments required to ensure safety of subjects should be administered as deemed necessary on a case by case basis. Under no circumstances including incidental collection is an investigator allowed to collect additional data or conduct any additional procedures for any purpose involving any investigational drugs under the protocol, other than the purpose of the study. If despite this interdiction prohibition, data, information, observation would be incidentally collected, the investigator shall immediately disclose it to Novartis and not use it for any purpose other than the study, except for the appropriate monitoring on study participants.

Investigators ascertain they will apply due diligence to avoid protocol deviations. If an investigator feels a protocol deviation would improve the conduct of the study this must be considered a protocol amendment, and unless such an amendment is agreed upon by Novartis and approved by the IRB/IEC and health authorities, where required, it cannot be implemented.

16.1 Appendix 1: Clinically notable laboratory values and vital signs

Alert criteria will be specified in the central laboratory documentation.

16.2 Appendix 2: Liver Event Definitions and Follow-up Requirements

Table 16-1 Liver Event Definitions

| Definition | Thresholds |
|--|---|
| Potential Hy's law cases | 
 ALT or AST $> 3 \times$ ULN and TBL $> 2 \times$ ULN without initial increase in ALP to $> 2 \times$ ULN |
| ALT or AST elevation with coagulopathy | 
 ALT or AST $> 3 \times$ ULN and INR > 1.5 (in the absence of anticoagulation) |
| ALT or AST elevation accompanied by symptoms | 
 ALT or AST $> 3 \times$ ULN accompanied by (general) malaise, fatigue, abdominal pain, nausea, or vomiting, or rash, or eosinophilia |
| Isolated ALT or AST elevation | 
 ALT or AST $> 8 \times$ ULN $5 \times$ ULN $<$ ALT/AST $\leq 8 \times$ ULN $3 \times$ ULN $<$ ALT/AST $\leq 5 \times$ ULN |
| Isolated ALP elevation | 
 ALP $> 2 \times$ ULN (in the absence of known pathology) |
| Others | 
 Any clinical event of jaundice (if not clearly PNH disease related) Any adverse event potentially indicative of liver toxicity |

Table 16-2 Actions required for Liver Events

| Criteria | Actions required |
|--|---|
| Potential Hy's Law case | |
| ALT or AST elevation with coagulopathy | 
 Discontinue the study treatment immediately (if not clearly PNH disease related) |
| ALT or AST elevation accompanied by symptoms | 
 Hospitalize, if clinically appropriate Establish causality |
| Isolated ALT or AST elevation $> 8 \times$ ULN | 
 Complete CRFs per liver event guidance* |
| Jaundice | 
 If confirmed, consider interruption or discontinuation of study drug |
| Isolated ALT or AST elevation > 5 to $\leq 8 \times$ ULN | 
 If elevation persists for more than 2 weeks, discontinue the study drug Establish causality Complete CRFs per liver event guidance* |
| Isolated ALT or AST elevation > 3 to $\leq 5 \times$ ULN (patient is asymptomatic) | 
 Monitor liver chemistry tests two or three times weekly |
| Isolated ALP elevation | 
 Repeat liver chemistry tests within 48-72 hours If elevation is confirmed, measure fractionated ALP; if $>50\%$ is of liver origin, establish hepatic causality Complete CRFs per liver event guidance* |
| Any AE potentially indicative of liver toxicity | 
 Consider study treatment interruption or discontinuation Hospitalize if clinically appropriate Complete CRFs per liver event guidance* |

*Liver event guidance for CRF completion is available in the Site Operations Manual

Table 16-3 Exclusion of underlying liver disease

| Disease | Assessment |
|--------------------------------|---|
| Hepatitis A, B, C, E | 
IgM anti-HAV; HBSAg, IgM anti-HBc, HBV DNA; anti-HCV, HCV RNA, IgM & IgG anti-HEV, HEV RNA |
| CMV, HSV, EBV infection | 
IgM & IgG anti-CMV, IgM & IgG anti-HSV; IgM & IgG anti-EBV |
| Autoimmune hepatitis | 
ANA & ASMA titers, total IgM, IgG, IgE, IgA |
| Alcoholic hepatitis | 
Ethanol history, GGT, MCV, CD-transferrin |
| Nonalcoholic steatohepatitis | 
Ultrasound or MRI |
| Hypoxic/ischemic hepatopathy | 
Medical history: acute or chronic CHF, hypotension, hypoxia, hepatic venous occlusion. Ultrasound or MRI. |
| Biliary tract disease | 
Ultrasound or MRI, ERCP as appropriate. |
| Wilson disease | 
Caeruloplasmin |
| Hemochromatosis | 
Ferritin, transferrin |
| Alpha-1-antitrypsin deficiency | 
Alpha-1-antitrypsin |

16.3 Appendix 3: Specific Renal Alert Criteria and Actions

Table 16-4 Specific Renal Alert Criteria and Actions

| Criteria | Action required |
|--|---|
| Serum creatinine (sCr) increase 25 – 49% compared to baseline | 
Consider causes and possible interventionsFollow up within 2-5 days |
| Serum creatinine increase \geq 50% | 
Consider causes and possible interventionsRepeat assessment within 24-48h if possibleConsider drug interruption or discontinuation unless other causes are diagnosed and correctedConsider hospitalization and specialized treatment |
| Protein-creatinine or albumin-creatinine ratio increase \geq 2-fold or new onset dipstick proteinuria \geq 1+ or Albumin-creatinine ratio (ACR) \geq 30 mg/g or \geq 3 mg/mmol; or Protein-creatinine ratio (PCR) \geq 150 mg/g or >15 mg/mmol | 
Consider causes and possible interventionsAssess serum albumin & serum proteinRepeat assessment to confirmConsider drug interruption or discontinuation unless other causes are diagnosed and corrected |
| New onset glucosuria on urine dipstick (unless related to concomitant treatment, diabetes) | Assess & document: 
Blood glucose (fasting)Serum creatinineUrine albumin-creatinine ratio |
| New hematuria on dipstick | Assess & document: 
Urine sediment microscopyAssess sCr and urine albumin-creatinine ratioExclude infection, trauma, bleeding from the distal urinary tract/bladder, menstruationConsider bleeding disorder |

Additional specialized assessments are available to assess renal function or renal pathology.
(Note: In exceptional cases when a nephrologist considers a renal biopsy, it is strongly recommended to make specimen slides available for evaluation by Novartis to potentially identify project-wide patterns of nephrotoxicity.)

Whenever a renal event is identified, a detailed subject history and examination are indicated to identify, document and potentially eliminate risk factors that may have initiated or contributed to the event:

- Blood pressure assessment (after 5 min rest, with an appropriate cuff size)
- Signs and symptoms such as fever, headache, shortness of breath, back or abdominal pain, dysuria, hematuria, dependent or periorbital edema
- Changes in blood pressure, body weight, fluid intake, voiding pattern, or urine output
- Concomitant events or procedures such as trauma, surgical procedures, cardiac or hepatic failure, contrast media or other known nephrotoxin administration, or other potential causes of renal dysfunction, e.g., dehydration, hemorrhage, tumor lysis

Table 16-5 Follow-up of renal events

| Action | Follow up |
|--|--|
| Assess*, document and record in the Case Report Form (CRF) or via electronic data load. Review and record possible contributing factors to the renal event (co-medications, other co-morbid conditions) and additional diagnostic procedures (MRI etc) in the CRF. | 
• Urine dipstick and sediment microscopy• Blood pressure and body weight• Serum creatinine, electrolytes (sodium, potassium, phosphate, calcium), bicarbonate and uric acid• Urine output• Event resolution: (sCr within 10% of baseline or protein-creatinine ratio within 50% of baseline) |
| Monitor subject regularly (frequency at investigator's discretion) until: | 
or
 
• Event stabilization: sCr level with $\pm 10\%$ variability over last 6 months or protein-creatinine ratio stabilization at a new level with $\pm 50\%$ variability over last 6 months. |

*Urine osmolality: in the absence of diuretics or chronic kidney disease this can be a very sensitive metric for integrated kidney function that requires excellent tubular function. A high urinary osmolality in the setting of an increase in sCr will point toward a “pre-renal” cause rather than tubular toxicity.

## 1 Introduction

### 1.1 Scope of document

The RAP documents contain detailed information to aid the production of Statistics & Programming input into the Clinical Study Report (CSR) for trial “**CLNP023X2204**”.

The Statistical analysis plan (SAP) describes the implementation of the statistical analysis planned in the protocol.

### 1.2 Study reference documentation

This SAP has been developed using the Clinical Trial Protocol version v02 (amended protocol) dated 03-Aug-2021.

### 1.3 Study objectives

#### 1.3.1 Primary objective(s)

Primary objective(s)	Endpoints related to primary objective(s)

To assess the effect of LNP023 on the reduction of PNH associated hemolysis.

	

Percentage of patients with 60% reduction in LDH or LDH below upper limit of normal (ULN) up to 12 weeks of treatment.

#### 1.3.2 Secondary objective(s)

Secondary objective(s)	Endpoints related to secondary objective(s)

To assess the dose-response effect of LNP023 on the reduction of PNH associated hemolysis

To assess the effect of LNP023 on markers of intravascular and extravascular hemolysis.

	

LDH, and other relevant parameters such as but not restricted to hemoglobin and red blood cell count up to week 4 for each dose.

Potentially all of, but not restricted to,

Total and free hemoglobin,

carboxyhemoglobin,

reticulocytes,

C3 fragment deposition,

haptoglobin,

bilirubin,

red blood cell count,

platelet counts,

ferritin,

PNH type III red blood cells (RBC)

PNH clone size.

• To assess the safety and tolerability of LNP023 in PNH patients.

	

• All safety parameters including: blood chemistry, hematology, urinalysis, ECG evaluation, vital signs, adverse events, transfusions, patient diary.

• To assess the plasma pharmacokinetics (PK) of LNP023

	

• Non-compartmental analysis of LNP023 PK parameters including, but not limited to Cmax, AUC, Ctrough and Tmax.

• To assess the effect of LNP023 on markers associated with risk of thrombosis.

	

• Assessments including, but not limited to, fibrinogen, prothrombin time, activated partial thromboplastin time, thrombin time, fibrin D-dimer and fibrinogen degradation products for fibrinolysis activity.

### **1.3.3 Exploratory objective(s)**

Exploratory objective(s)	Endpoints related to exploratory objective(s)
Commercially Confidential Information	

### **1.4 Study design and treatment**

This is a non-confirmatory, randomized, open-label, multicenter, efficacy, safety, pharmacokinetic and pharmacodynamic study assessing CCI LNP023 doses, in adult PNH patients with active hemolysis.

At least 10 patients will be included in the study, as replacement can occur if any patient withdraws for reasons unrelated to safety or lack of efficacy.

Total study duration from screening until EOS is approximately 2.5 years. This three-period study includes: a screening phase of up to 8 weeks, a baseline visit, Day 1 (first day that the investigational drug is given), a 4-week treatment period of LNP023 at the first dose in the assigned sequence (Period 1), an 8-week treatment period at the second dose in the assigned sequence (Period 2), an approximately 2 year extension Period 3, followed by a taper down period of 2 weeks, an end of study visit and a safety follow up call performed 30 days post end of treatment.

Patient will be randomized to sequence 1 or sequence 2 in ratio 1:1.

Commercially Confidential Information

**Figure 1-1      Study design and dosing schema**

Commercially Confidential Information

## **2 First interpretable results (FIR)**

No FIR will be produced for the final analysis.

## **3 Interim analyses**

Commercially Confidential Information

## **4 General considerations**

The final study analysis will be conducted on all patients' data at the time the trial ends.

Commercially Confidential Information

## **5 Statistical methods: Analysis sets**

For all analysis sets, subjects will be analyzed according to the study treatment(s) received. This implies that for subjects for whom the actual treatment received does not match the randomized treatment, the treatment actually received will be used for the analysis.

The Full Analysis Set (FAS) comprises all patients that received any study drug.

The Safety analysis set will also include all patients that received any study drug and hence is not referred to again.

The PK analysis set will include all subjects with at least one available valid (i.e. not flagged for exclusion) PK concentration measurement, who received any study drug and with no protocol deviations that impact on PK data.

The PD analysis set will include all subjects with available PD data, who received any study drug and with no protocol deviations with relevant impact on PD data.

The analysis sets and protocol deviation codes are related as follows:

**Table 5-1 Protocol deviation codes and analysis sets**

Category Deviation code	Text description of deviation	Data exclusion
	Subjects are excluded from all ( safety and FAS ) analysis in case of these protocol deviations:	Exclude subject completely from all ( safety and FAS ) analysis sets
	Subjects are excluded from PK analysis in case of these protocol deviations: INCL01	Exclude subject from PK analysis set
	Subjects are excluded from PD analysis in case of these protocol deviations: INCL01	Exclude subject from PD analysis set
	Subjects are excluded from PK and PD analysis in case of these protocol deviations: INCL01	Exclude subject from PK and PD analysis sets

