5.1 Inclusion criteria

Subjects eligible for inclusion in this study must meet **all** of the following criteria:

1. Written informed consent must be obtained before any assessment is performed.
2. Male and female patients at least 18 years old at baseline.
3. Diagnosis of active PNH based on documented clone size of $\geq 10\%$ by RBCs and/or granulocytes, measured by GPI-deficiency on flow cytometry (screening or medical history data acceptable).

4. LDH values $\geq 1.5 \times$ upper limit of the normal range (ULN) for at least 3 measurements over a maximum of 8 weeks prior to Day 1 (Screening, baseline or medical history data acceptable).
5. Hemoglobin level $< 10.5 \text{ g/dL}$ at Baseline.
6. For Period 3 of the study, patients who as per judgment of Investigator benefit from LNP023 treatment based on reduced hemolytic parameters as compared to Screening and Baseline.
7. Vaccinations against *N. meningitidis*, *S. pneumoniae* and *H. influenzae* is required at least 4 weeks prior to first dosing with LNP023 (existing vaccinations should provide effective titers at time of LNP023 treatment start). If LNP023 treatment has to start earlier than 4 weeks post vaccination, prophylactic antibiotic treatment must be initiated.
8. Able to communicate well with the investigator, to understand and comply with the requirements of the study.

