## 7 Statistical methods for Pharmacodynamic (PD) parameters

All subjects within the PD analysis set will be included in the PD data analysis.

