#### 7.1.2 Descriptive analyses

Frequency tabulations reporting number and percentage of responders by week 12 by randomized sequence. Frequency tables will also be summarized by dose over time as described in [Section 4](#).

There is no statistical model for the primary endpoint apart from observing and counting success or failure for each patient. For the purposes of this study a positive sign of efficacy is when the estimated response rate is at least 50%. For example, this criterion will be met when at least 5 out of 10 patients in the overall study, or 3 of 5 in one of the two Cohorts are considered responders.

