#### 7.1.2.1 Handling of missing values/censoring/discontinuations

For calculation of the success rate for the primary endpoint all patients enrolled in the study apart from those who were replaced for reasons other than safety or efficacy will be included in the denominator.

Commercially Confidential Information

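### SAP Section 7 with Table 5-1 takes INCL01 patients out of the primary response analysis, while SAP 7.1.2.1 and Protocol 12.4.3 keep them in the denominator

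*SAP*

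**What the plan says.** Four places in the SAP bear on who counts in the primary analysis.

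- SAP Section 5 defines the PD set by data availability, dosing and deviations that affect PD results: "The PD analysis set will include all subjects with available PD data, who received any study drug and with no protocol deviations with relevant impact". The PK set has a matching condition for deviations that affect PK data. The FAS is every patient who received study drug.
- SAP Table 5-1 is presented as the link between deviation codes and sets. Its PD row reads "Subjects are excluded from PD analysis in case of these protocol deviations: INCL01". The PK row and the combined PK and PD row carry the same single code.
- SAP Section 7 opens with "All subjects within the PD analysis set will be included in the PD data analysis". The primary objective is Section 7.1, inside that section.
- SAP 7.1.2.1 sets the primary denominator differently: "all patients enrolled in the study apart from those who were replaced for reasons other than safety or efficacy will be included in the denominator". Protocol 12.4.3 has the same rule.

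The first inclusion criterion in Protocol 5.1 is "Written informed consent must be obtained before any assessment is performed".

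**The concern.** The primary result is a bare count of responders judged against a 50% cut in about 10 patients, so the denominator is most of the analysis. Two visible rules give different denominators for the same patient, and no visible text says which prevails.

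The excluding rule also does not follow from its own definition. Section 5 removes patients because a deviation affects the data. If INCL01 is the consent criterion, the deviation does not change an LDH value or a plasma concentration. There may be a reason not to use data collected without valid consent, but that would be a data-use reason, and the SAP does not state it. As written, a programmer following Table 5-1 and one following 7.1.2.1 could report different response rates, and the choice could be made after the open-label results are known.

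**Working it through.** **Which criterion INCL01 is.** The documents contain no code list. SAP 7.2.1 (partial exclusion of data) removes hemoglobin records for an INCL05 deviation, and inclusion criterion 5 in Protocol 5.1 is the hemoglobin criterion. On that match INCL01 is inclusion criterion 1, written consent. This is an inference.

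**The rules side by side**, for a patient who was dosed, not replaced, and has an INCL01 deviation:

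| Rule | Patient in the primary analysis? |
|---|---|
| SAP 7 opening sentence with Table 5-1 | No |
| SAP 7.1.2.1 | Yes |
| Protocol 12.4.3 | Yes |

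The replacement exception in 7.1.2.1 does not cover INCL01 as such, so it does not remove the conflict.

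**The plan's own figure.** Protocol 12.8.1 states: "With 10 subjects this study has 80% probability to meet the efficacy criteria of 5 or more successful patients out of 10", taking a true response rate of 58%. With X ~ Binomial(10, 0.58), P(X ≥ 5) = 0.798. The stated 80% is reproduced.

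**One exclusion.** The number of INCL01 patients is not given, so one is assumed, with exclusion independent of response. With n = 9 the 50% cut needs 5 responders (4/9 = 44.4%; 5/9 = 55.6%). With Y ~ Binomial(9, 0.58), P(Y ≥ 5) = 0.690. The probability of success falls from 79.8% to 69.0%.

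The whole loss comes from one configuration: the excluded patient responded and exactly 4 of the other 9 did.

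- Before: 5/10 = 50.0%, positive.
- After: 4/9 = 44.4%, not positive.
- Chance: 0.58 × C(9,4) × 0.58⁴ × 0.42⁵ = 0.108, which equals 0.798 − 0.690.

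In the other direction, 4/10 (40.0%) becomes at best 4/9 (44.4%). With 10 patients, one exclusion cannot make a negative overall count positive.

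**Two exclusions**, same assumptions: n = 8 needs 4 responders, and P = 0.794. The probability is almost unchanged, but the result can now move both ways:

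- 5/10 to 3/8 (two responders lost): 0.58² × C(8,3) × 0.58³ × 0.42⁵ = 0.048.
- 4/10 to 4/8 (two non-responders lost): 0.42² × C(8,4) × 0.58⁴ × 0.42⁴ = 0.043.

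**Limit of these figures.** They use the overall-study count, as Protocol 12.8.1 does. SAP 7.1.2 also gives 3 of 5 in one cohort as an example of meeting the criterion. If that is a separate route to a positive result, and the cohorts are the two sequences of five, the effect differs. A 5/10 trial split 3/5 and 2/5 that loses a responder keeps a cohort at 50% or more (2/4 or 3/5). A cohort at 2/5 (40%) that loses a non-responder becomes 2/4 (50%).

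**The case against.** The strongest reply is that 7.1.2.1 is the specific rule for this endpoint, repeats the protocol, and so governs over a general opening sentence. That is the sensible reading and probably the intended one. But the SAP does not say so, and Section 7 makes no visible exception for 7.1. Section 4 and the text after the 7.1.2.1 rule are partly redacted, so a clarifying sentence may exist there.

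It is also fair to say that the study is non-confirmatory and has no hypothesis test, that Protocol 11.3 requires full verification of consent so INCL01 deviations should be rare, and that the one-patient flip on the overall count is in the conservative direction. These points limit the size of the problem but leave the contradiction in place.

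A reader might infer two stronger points that the documents do not support.

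- *That the PD set drops dosed patients without post-dose LDH and so removes failures.* Section 5 asks for available PD data, not post-dose data. Eligibility requires at least one central-laboratory LDH value (Protocol 3). SAP 7.1.1 makes anyone meeting neither response criterion a non-responder, and 7.1.2.1 keeps that patient in the denominator.
- *That data after missed doses or prohibited medication must stay in because Table 5-1 has no code for them.* Section 5 excludes by impact in general terms, allows individual PK concentrations to be flagged, and the INCL05 rule shows that exclusions can sit outside the table.

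Nor should weight be put on the row for exclusion from all sets appearing empty, since cells may have been lost in reading the PDF.

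**Conclusion.** The concern holds in a limited form. Two stated rules give different primary denominators for a dosed, unreplaced INCL01 patient, and the excluding code does not fit the ground that Section 5 gives for it.

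On the overall count with 10 patients, one exclusion can turn a 50.0% result into 44.4%, and it lowers the probability of success at a 58% rate from 79.8% to 69.0%. These figures are illustrations. They assume one INCL01 patient, exclusion independent of response, and the overall-study criterion. The reading of INCL01 as consent rests on the numbering, but the denominator conflict stands whatever the code means, provided the patient was dosed and not replaced. Nothing in the documents shows that any such patient exists. The point should be settled before database lock.

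**What to change.** 1. In SAP 7.1, state that the primary response analysis uses the FAS, subject only to the replacement rule in 7.1.2.1, with non-response as already defined in 7.1.1.
2. Limit the PD-set sentence that opens Section 7 to the secondary and exploratory PD analyses.
3. Reconcile the three INCL01 rows of Table 5-1 with Section 5. Either remove INCL01 from the PK, PD and combined rows, or, if lack of valid consent bars use of the data, call it a data-use exclusion, apply it to every set, and write it into 7.1.2.1. Moving the code to the all-sets row without changing 7.1.2.1 would recreate the conflict. If this second option is taken, record it as a departure from Protocol 12.4.3.
4. State in the SAP which inclusion criterion each deviation code denotes.

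The cost is a few sentences and a revised table before database lock. No new data are needed and the sample size is unaffected.
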